**11.7. Efficacy Listings**

Efficacy listings will include data specified in [Table 15](#) for all subjects presented by subject number and treatment group.

**Table 15: Data Presented in Efficacy Listings**

Listing	Data Presented
Time to Symptom Response	Date/time of first dose Date/time of Symptom Response Event time (hours) Censored time (hours)
Time to Ability to Perform All Normal Activities	Date/time of first dose Date/time of Ability to Perform All Normal Activities Event time (hours) Censored time (hours)

Listing	Data Presented
Complications of Colds	MedDRA SOC MedDRA preferred term Reported term Onset date End date Severity Outcome Change in study drug dosage Treatment required
Time to Individual Symptom Response	Date/time of first dose Date/time of Individual Symptom Response Event time (hours) Censored time (hours)
Time to FLU-PRO Domain Response	Date/time of first dose Date/time of FLU-PRO Domain Response Event time (hours) Censored time (hours)
Time to Return to Usual Health	Date/time of first dose Date/time of Return to Usual Health Event time (hours) Censored time (hours)
Virology Data	Study day RT-PCR result Quantitative PCR result

## 12. SAFETY

### 12.1. Safety Tables and Figures

Unless otherwise specified, all safety tables will be based on the ITT population and present data by treatment group.

Adverse events summary tables will use the following algorithms for counting subject events:

- Preferred term: Each subject will be counted once within each unique preferred term at the maximum grade.
- System organ class: Each subject is counted only once at the maximum grade at each system organ class level.
- Any event: Each subject with an event is counted only once at the maximum grade.

### **12.1.1. Summary of All Treatment Emergent Adverse Events (TEAEs)**

The summary of all TEAEs will summarize the following:

- The total number of TEAEs;
- The number and percentage of subjects with at least one TEAE;
- The number and percentage of subjects with at least one SAE;
- The number and percentage of subjects with a TEAE by the maximum severity grade; and
- The number and percentage of subjects with a TEAE by the closest relationship to the study drug.

### **12.1.2. Summaries of TEAEs by SOC and Preferred Term**

The number and percent of subjects with TEAEs will be summarized by SOC and preferred term with the following variations in presentation

- Number and percent of subjects with TEAEs will be summarized by SOC and preferred term;
- Number and percent of subjects with TEAEs will be summarized by SOC, preferred term and severity;
- Number and percent of subjects with grade  $\geq 3$  TEAEs by SOC and preferred term;
- Number and percent of subjects with TEAEs by SOC, preferred term and relationship to study medication;
- Number and percent of subjects with unexpected TEAEs by SOC and preferred term (Note: unexpected TEAEs are those not listed in the Investigator's Brochure for the study);
- Number and percent of subjects with SAEs by SOC and preferred term; and
- Number and percent of TEAEs leading to study withdrawal by SOC and preferred term.

### **12.1.3. Laboratory Results and Changes from Baseline**

Numerical hematology and serum biochemistry values will be converted to SI units and classified as Normal, Grade 1, Grade 2, Grade 3 or Grade 4 according to reference ranges indicated in the protocol toxicity grading scale tables (see Protocol Appendix II). Urinalysis results will be classified as Normal or Abnormal based on reference ranges provided by the central laboratory.

Hematology, serum biochemistry, and urinalysis laboratory results and change from Baseline will be summarized using descriptive statistics for each visit.

Shift tables will display shifts from Baseline in laboratory results classification (Grade 1/2/3/4 or Normal/Abnormal) by study day.

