5.11. Plan for Laboratory Safety Tests

A central laboratory will be used for laboratory safety testing. Blood tests will include hemoglobin, hematocrit, complete blood count (total and differential), platelet count, random blood sugar, total cholesterol, HDL, LDL, triglycerides, albumin, AST, ALT, GGT, alkaline phosphatase, bilirubin (total/direct), BUN, creatinine, sodium, potassium, chloride. Routine urinalysis will include glucose, protein, and blood.

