** Derived from the National Institutes of Health, National Cancer Institute Common Terminology Criteria for Adverse Events (CTCAE) Version 4.0. ADL- Activities of Daily Living refer to preparing meals, shopping for groceries or clothes, using the telephone, managing money, etc. selfcare ADL refer to bathing, dressing and undressing, feeding self, using the toilet, taking medications, and not bedridden.

*** "ULN" is the upper limit of the normal range.

Table 19: Table for Laboratory Abnormalities: Urine

Urine*	Mild (Grade 1)	Moderate (Grade 2)	Severe (Grade 3)	Potentially Life Threatening (Grade 4)
Protein	Trace	1+	2+	Hospitalization or dialysis
Glucose	Trace	1+	2+	Hospitalization for hyperglycemia
Blood (microscopic) – red blood cells per high power field (rbc/hpf)	1 – 10	11 – 50	> 50 and/or gross blood	Hospitalization or packed red blood cells (PRBC) transfusion

* The laboratory values provided in the tables serve as guidelines and are dependent upon institutional normal parameters. Institutional normal reference ranges should be provided to demonstrate that they are appropriate.

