14.3.1.8	Number and Percent of Subjects with Treatment Emergent Adverse Events Leading to Study Withdrawal by System Organ Class and Preferred Term	Table	ITT
14.3.2.1	Summary of Hematology Laboratory Results and Changes from Baseline	Table	ITT
14.3.2.2	Change in Hematology Laboratory Results Over Time: Shift Table	Table	ITT
14.3.3.1	Summary of Serum Biochemistry Laboratory Results and Changes from Baseline	Table	ITT
14.3.3.2	Change in Serum Biochemistry Laboratory Results Over Time: Shift Table	Table	ITT
14.3.4.1	Number and Percent of Subjects with Each Urinalysis Result	Table	ITT
14.3.4.2	Change in Urinalysis Results Over Time: Shift Table	Table	ITT
14.3.5.1	Summary of Vital Signs Results and Change from Baseline	Table	ITT
14.3.5.2	Change in Vital Signs Results Over Time: Shift Table	Table	ITT
14.3.6.1	Summary of Physical Examination Results by Category	Table	ITT
14.3.6.2	Number and Percent of Subjects with Physical Examination Changes from Normal at Baseline to Abnormal by Category	Table	ITT

*Listings*

16.2.1	Listing of Discontinued Subjects	Listing	ITT
16.2.2	Listing of Subjects with Protocol Deviations	Listing	ITT
16.2.3	Listing of Subjects Excluded from Efficacy Analysis	Listing	ITI
16.2.4.1	Listing of Demographic Data	Listing	ITT
16.2.4.2	Listing of Baseline Disease Characteristics	Listing	ITT
16.2.4.3	Listing of Prior Medication	Listing	ITT
16.2.4.4	Listing of Concomitant Medication	Listing	ITT
16.2.4.5	Listing of Medical History	Listing	ITT
16.2.4.6	Listing of Concomitant Diseases	Listing	ITT
16.2.5	Listing of Treatment Exposure Data	Listing	ITT
16.2.6.1	Listing of Time to Symptom Response	Listing	ITI
16.2.6.2	Listing of Time to Ability to Perform All Normal Activities	Listing	ITI
16.2.6.3	Listing of Complications of Colds	Listing	ITI
16.2.6.4	Listing of Time to Individual Symptom Response	Listing	ITI
16.2.6.5	Listing of Time to FLU-PRO Domain Response	Listing	ITI
16.2.6.6	Listing of Time to Return to Usual Health	Listing	ITT
16.2.6.7	Listing of Time to Symptom Response for All Subjects Treated	Listing	ITT

Display Number	Title	Type	Analysis Population
16.2.6.8	Listing of Time to Symptom Response for Specific Virus Subgroups	Listing	ITT
16.2.6.9	Listing of Virology Data	Listing	ITT
16.2.7	Listing of Adverse Events	Listing	ITT
16.2.8.1	Listing of Hematology Laboratory Results	Listing	ITT

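### The SAP's urinalysis shift table uses a Normal/Abnormal split although the protocol grades the same tests, so it hides 2 or 3 of the 6 possible worsenings in urine protein or glucose

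*SAP*

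**What the plan says.** **Classification.** SAP 12.1.3 has hematology and serum values "classified as Normal, Grade 1, Grade 2, Grade 3 or Grade 4 according to reference ranges indicated in the protocol toxicity grading scale tables". For urine it says: "Urinalysis results will be classified as Normal or Abnormal based on reference ranges provided by the central laboratory". It gives no reason for the difference. SAP 12.1.4 also uses the Appendix II grades for vital signs.

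**Shift tables.** The same section states: "Shift tables will display shifts from Baseline in laboratory results classification (Grade 1/2/3/4 or Normal/Abnormal) by study day". For urine, therefore, the shift is between two classes.

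**Protocol scale.** Protocol 5.11 states: "Routine urinalysis will include glucose, protein, and blood". Appendix II contains "Table 19: Table for Laboratory Abnormalities: Urine", which covers those three tests. Protein and glucose are Grade 1 at trace, Grade 2 at 1+ and Grade 3 at 2+. Blood is graded by microscopy count per high-power field: 1-10, 11-50, and above 50 or gross blood. Grade 4 is a clinical outcome for all three tests; for protein it reads "Hospitalization or dialysis".

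**Planned urine outputs.** SAP Appendix 2 (Table 18) lists three:
- display 14.3.4.1, "Number and Percent of Subjects with Each Urinalysis Result";
- shift table 14.3.4.2;
- listing 16.2.8.3, which by SAP Table 16 shows each subject's result at each visit with a low/normal/high flag.

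**The concern.** A shift table shows how far individual subjects moved, separately by treatment group. With two classes, every worsening that crosses the laboratory's limit falls in the single Normal-to-Abnormal cell, whatever its size. Every worsening that stays on one side of the limit counts as no change.

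Urine is scheduled only at Baseline and Day 7 (Protocol 5.2 and 5.6), so this one comparison carries the planned information on change. If the groups differed in how severe new urinary findings were, or in how often an existing finding worsened, the table could fail to show it. The protocol already holds a finer scale for these tests. Among the measured panels that Appendix II grades, urine is the only one for which the SAP leaves that scale unused.

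**Working it through.** The plan gives no figure to reproduce, and safety analysis is descriptive (Protocol 8.4.3), so power and alpha do not enter. The check is to count which worsenings a two-level table can show.

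**Inputs**
- Levels for protein and glucose, from Protocol Table 19: negative, trace (Grade 1), 1+ (Grade 2), 2+ (Grade 3). Grade 4 is left out because it is not a urinalysis result.
- Position of the Normal/Abnormal cut: set by the central laboratory and not given in the documents, so every possible position is tried.

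**Step 1: possible worsenings.** Four ordered levels give 3 + 2 + 1 = 6 upward moves.

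**Step 2: what a cut shows.** If m levels are Normal and n are Abnormal (m + n = 4), a worsening is visible only when it starts in one of the m and ends in one of the n. Visible = m × n; hidden = 6 − m × n.

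| Abnormal starts at | m × n | Visible | Hidden | Moves hidden |
|---|---|---|---|---|
| Trace | 1 × 3 | 3 | 3 | Trace to 1+; trace to 2+; 1+ to 2+ |
| 1+ | 2 × 2 | 4 | 2 | Negative to trace; 1+ to 2+ |
| 2+ | 3 × 1 | 3 | 3 | Negative to trace; negative to 1+; trace to 1+ |

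**Step 3: reading the result.** No cut shows all six; 2 or 3 are always hidden. The move from 1+ to 2+ (Grade 2 to Grade 3) is hidden under two of the three cuts. The 3 or 4 visible moves share one cell, so their size is not shown either.

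**Step 4: the proposed classification.** With Normal, Grade 1, Grade 2 and Grade 3 as classes, all 6 moves are visible and each has its own cell.

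**Step 5: blood.** Table 19 gives blood the same number of laboratory grades, but in counts per high-power field. The documents do not say that the routine urinalysis reports such counts, so the result carries over to blood only if it does.

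**The case against.** **The results are not lost.** Display 14.3.4.1 counts subjects at each result level, and listing 16.2.8.3 lets a reader follow any one subject from Baseline to Day 7. This stands, and it limits the point. But the counts, as titled, do not pair the two visits within a subject, and a listing does not summarize by treatment group.

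**SAP 12.1.3 also plans descriptive change from Baseline for urinalysis.** This is true, so the shift table is not the only planned text on change. However, Table 18 has displays titled for results and changes only for hematology (14.3.2.1) and serum (14.3.3.1). How urine change would be shown, apart from the shift table, is left open.

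**The protocol does not ask for graded laboratory shifts.** Appendix II is a scale for adverse-event severity, and its footnote to Table 19 calls the values guidelines that depend on institutional norms. This stands: using laboratory ranges is permissible. It does not explain the difference in treatment, because Tables 17 and 18 carry the same footnote and the SAP still uses their grades. Physical examination shifts are also two-level (SAP 12.1.5), but Appendix II has no table of examination findings to apply.

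**Stronger readings that the documents do not support.** A reader might infer that a move from trace to 2+ would show as no shift. That holds only if the laboratory flags trace as Abnormal; under the other two cuts it appears as Normal to Abnormal. A reader might also infer that the Grade 3 stopping rule is weakened. Protocol 11.1 applies that rule to adverse events judged related to study drug, and the investigator grades their severity with Appendix II (Protocol 10.1). The shift table plays no part in it.

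**Conclusion.** The point holds as a minor gap in descriptive safety output. For urine protein and glucose, shift table 14.3.4.2 hides 2 or 3 of the 6 worsenings that laboratory results can show on the protocol's own scale. It also merges the visible ones into one cell.

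This rests on two things: the four levels in Table 19, and a Normal/Abnormal limit lying somewhere among them. It does not depend on which limit the laboratory uses, except for which moves are hidden. For blood it also depends on microscopy counts being reported.

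The effect cannot be sized in subjects, because the documents give no rate of abnormal urine results at Baseline or Day 7. It would also be wrong to call this a breach of the protocol or to say that worsening cannot be found anywhere: the listing shows it subject by subject. What is missing is the treatment-group summary of how severe the change was.

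**What to change.** In SAP 12.1.3, classify urine protein and glucose as Normal or Grade 1 to 3 by Protocol Table 19, and do the same for blood where counts per high-power field are reported. Build shift table 14.3.4.2 on those grades, and keep the central-laboratory flag in listing 16.2.8.3. Table 19 names no level above 2+, so the sentence should also say how any higher reading is classed. If the sponsor prefers two levels, the SAP should say why and state the laboratory's limit for each test.

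The cost is about one SAP sentence and a small recode. Protein and glucose need no new data if they are reported on the trace/1+/2+ scale that Table 19 uses. The downside is that blood stays Normal/Abnormal if microscopy counts are not available, so the three urine tests might not share one scale.

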#### 12.1.4. Summaries of Vital Signs Results and Changes from Baseline

Vital signs data will be classified as Normal, Grade 1, Grade 2, Grade 3 or Grade 4 based on the reference ranges indicated in the protocol toxicity grading scale tables (see Protocol Appendix II). If two vital signs values are available in the database for one analysis time point (e.g., Day 7 Visit), the later value will be used for the analysis.

Vital signs results and change from Baseline will be summarized using descriptive statistics for each visit.

Shift tables will display shifts from Baseline in vital signs classification (Grade 1/2/3/4) by study day.

#### 12.1.5. Summaries of Physical Examination Results and Changes from Baseline

The number and percent of subjects with abnormal physical examination findings will be summarized by body system for each visit.

A shift table will display changes in physical examination classification (Normal/Abnormal) at each visit by body system.

### 12.2. Safety Listings

Safety listings will include data specified in [Table 16](#) for all subjects presented by subject number and treatment group.

**Table 16: Data Presented in Safety Listings**

Listing	Data Presented
Adverse Events	MedDRA SOC MedDRA preferred term Reported term Onset date End date Severity Serious (Y/N) Relation to study drug Outcome Change in study drug dosage Treatment required
Hematology Laboratory Results Serum Biochemistry Laboratory Results Urinalysis Laboratory Results	Visit Date of visit Laboratory test Result Result units Lower limit of normal Upper limit of normal Classification (L/N/H)

Listing	Data Presented
Plasma Tizoxanide and Tizoxanide Glucuronide Results	Visit Date of visit Tizoxanide concentration (µg/mL) Tizoxanide glucuronide concentration (µg/mL)
Vital Signs Data	Visit Date of visit Weight (kg) Systolic blood pressure (mmHg) Diastolic blood pressure (mmHg) Pulse (bpm) Respiratory rate (bpm) Oral temperature (°F)
Physical Examination Data	Visit Date of visit Body system Result (Normal/Abnormal/Not Done) Abnormality

**APPENDIX 1. SCHEDULE OF ASSESSMENTS****Table 17: Schedule of Assessments**

	Screening (Day 1)	Baseline (Day 1)	Days 2-22	Days 2-5	Days 2, 3	Day 7 	Day 22+3	Unscheduled Visit
Signed informed consent	X							
Complete medical history	X							
Physical examination/weight/vital signs	X					X 	X 	X
Demographics/smoking history	X							
Urine pregnancy test	X							
Record oral temperature	X					X	X	X
Record symptoms and time of onset	X							
Evaluate according to inclusion/exclusion criteria	X							
Collect nasopharyngeal swabs		X			X 	X 	X 	X
Blood sample for pharmacokinetics					X 			
Blood sample for laboratory safety tests 	X					X		X
Urine sample for routine urinalysis 	X					X		X
Record concomitant medications	X					X	X	X
Complete Baseline symptoms in diary and dispense diary		X						
Randomization/dispense study medication		X						
First dose in office and enter in diary		X						
Instructions re: dosing, concomitant medications, subject diary, birth control, follow-up visits and seeking emergency care		X		X		X		X
Review/record adverse events	X			X	X	X	X	X
Review electronic subject diary entries			X 					X 
Screen for EV-related complications				X	X			
Review compliance with study medication, collect container with unused medication, complete pill count log form					X	X		X 

 Day 7 and 22 physical exam is a brief physical exam (vital signs and nursing physical assessment) including symptom directed physician physical examination as required by subject symptoms. Vital signs include blood pressure, pulse, respiratory rate and oral temperature.

 Nasopharyngeal swabs on days 2 and 3 will be collected at the subject's home (or clinic or another location as agreed with the subject).

 Nasopharyngeal swabs collected on day 7 will only be tested for the presence of virus if a sample from day 1, 2 or 3 was positive for enterovirus/rhinovirus.

 Nasopharyngeal swabs collected on day 22 will only be tested for the presence of virus if the sample from day 7 was positive for enterovirus/rhinovirus.

 Blood sample collected pre-dose on day 3.

 Laboratory safety tests include hemoglobin, hematocrit, complete blood count (total and differential), platelet count, random blood sugar, total cholesterol, HDL, LDL, triglycerides, albumin, AST, ALT, GGT, alkaline phosphatase, bilirubin (total/direct), BUN, creatinine, sodium, potassium, chloride and routine urinalysis (glucose, proteins and blood).

 All subjects will maintain an electronic diary until day 22 (+3). Site staff will contact subjects as needed during study to ensure timely completion of electronic diary.

 Collection of unused IMP and completion of pill count log form will be performed at unscheduled visit if applicable

## APPENDIX 2. DATA DISPLAYS

**Table 18: Data Displays**

Display Number	Title	Type	Analysis Population
General Displays			
14.1.1.1	Disposition of Subjects	Table	ITT
14.1.1.2	Disposition of Subjects	Table	ITTI
14.1.2.1	Summary of Protocol Deviations	Table	ITT
14.1.2.2	Summary of Protocol Deviations	Table	ITTI
14.1.3.1	Summary of Baseline Demographic Characteristics	Table	ITT
14.1.3.2	Summary of Baseline Demographic Characteristics	Table	ITTI
14.1.4.1	Summary of Baseline Disease Characteristics	Table	ITT
14.1.4.2	Summary of Baseline Disease Characteristics	Table	ITTI
14.1.5.1	Summary of Prior Medication	Table	ITT
14.1.5.2	Summary of Prior Medication	Table	ITTI
14.1.6.1	Summary of Concomitant Medication	Table	ITT
14.1.6.2	Summary of Concomitant Medication	Table	ITTI
14.1.7.1	Summary of Medical History	Table	ITT
14.1.7.2	Summary of Medical History	Table	ITTI
14.1.8.1	Summary of Concomitant Diseases	Table	ITT
14.1.8.2	Summary of Concomitant Diseases	Table	ITTI
14.1.9.1	Summary of Treatment Exposure	Table	ITT
14.1.9.2	Summary of Treatment Exposure	Table	ITTI
Efficacy Displays			
14.2.1.1	Evaluation of Symptom Response Definitions	Table	ITTI
14.2.1.2	Analysis of Time to Symptom Response	Table	ITTI
14.2.1.3	Graphical Representation of Time to Symptom Response	Figure	ITTI
14.2.2.1.1	Sensitivity Analysis of Time to Symptom Response Assigning a Time to Symptom Response of 21 Days to Discontinued Subjects	Table	ITTI
14.2.2.1.2	Graphical Representation of Sensitivity Analysis of Time to Symptom Response Assigning a Time to Symptom Response of 21 Days to Discontinued Subjects	Figure	ITTI
14.2.2.2.1	Sensitivity Analysis of Time to Symptom Response for the Per Protocol Population	Table	Per Protocol

Display Number	Title	Type	Analysis Population
14.2.2.2.2	Graphical Representation of Sensitivity Analysis of Time to Symptom Response for the Per Protocol Population	Figure	Per Protocol
14.2.2.3.1	Sensitivity Analysis of Time to Symptom Response Excluding NTZ-treated Subjects Reporting Chromaturia	Table	ITTI
14.2.2.3.2	Graphical Representation of Sensitivity Analysis of Time to Symptom Response Excluding NTZ-treated Subjects Reporting Chromaturia	Figure	ITTI
14.2.3.1	Analysis of Time to Ability to Perform All Normal Activities	Table	ITTI
14.2.3.2	Graphical Representation of Time to Ability to Perform All Normal Activities	Figure	ITTI
14.2.4	Analysis of Proportions Experiencing Complications of Colds	Table	ITTI
14.2.5.1.x	Analysis of Time to Individual Symptom Response	Table	ITTI
14.2.5.2.x	Graphical Representation of Time to Individual Symptom Response	Figure	ITTI
14.2.6.1.x	Analysis of Time to FLU-PRO Domain Response	Table	ITTI
14.2.6.2.x	Graphical Representation of Time to FLU-PRO Domain Response	Figure	ITTI
14.2.7.1	Analysis of Time to Return to Usual Health	Table	ITTI
14.2.7.2	Graphical Representation of Time to Return to Usual Health	Figure	ITTI
14.2.8	Analysis of Changes in EV/RV Virus Titer	Table	ITTI
14.2.9	Proportions of Subjects with Detectable EV/RV on Days 2, 3, and 7	Table	ITTI
14.2.10.1	Exploratory Evaluation of Symptom Response Definitions for All Subjects Treated	Table	ITT
14.2.10.2.1	Analysis of Time to Symptom Response for All Subjects Treated	Table	ITT
14.2.10.2.2	Analysis of Time to Ability to Perform All Normal Activities for All Subjects Treated	Table	ITT
14.2.10.2.3	Analysis of Proportions Experiencing Complications of Colds, All Subjects Treated	Table	ITT
14.2.10.3.1	Graphical Representation of Time to Symptom Response for All Subjects Treated	Figure	ITT
14.2.10.3.2	Graphical Representation of Time to Ability to Perform All Normal Activities for All Subjects Treated	Figure	ITT
14.2.11.x.1	Exploratory Evaluation of Symptom Response Definitions for Specific Virus Subgroups	Table	ITT
14.2.11.x.2	Analysis of Time to Symptom Response for Specific Virus Subgroups	Table	ITT
14.2.11.x.3	Graphical Representation of Time to Symptom Response for Specific Virus Subgroups	Figure	ITT
14.2.12.1.1	Analysis of Time to Symptom Response for Subjects Dosed $\leq$ 24 Hours from Symptom Onset	Table	ITTI
14.2.12.1.2	Graphical Representation of Time to Symptom Response for Subjects Dosed $\leq$ 24 Hours from Symptom Onset	Figure	ITTI
14.2.12.2.1	Analysis of Time to Symptom Response for Subjects Dosed $>24 - \leq 36$ Hours from Symptom Onset	Table	ITTI
14.2.12.2.2	Graphical Representation of Time to Symptom Response for Subjects Dosed $>24 - \leq 36$ Hours from Symptom Onset	Figure	ITTI
14.2.12.3.1	Analysis of Time to Symptom Response for Subjects Dosed $>36$ Hours from Symptom Onset	Table	ITTI

Display Number	Title	Type	Analysis Population
14.2.12.3.2	Graphical Representation of Time to Symptom Response for Subjects Dosed >36 Hours from Symptom Onset	Figure	ITTI
14.2.13	Analysis of Plasma Tizoxanide and Tizoxanide Glucuronide Concentrations	Table	ITTI
14.2.14.1.1	Analysis of Time to Symptom Response by Symptom Relief Medication Use, Placebo-Treated Subjects	Table	ITTI
14.2.14.1.2	Graphical Representation of Time to Symptom Response by Symptom Relief Medication Use, Placebo-Treated Subjects	Figure	ITTI
14.2.14.1.3	Analysis of Time to Symptom Response by Symptom Relief Medication Use, Placebo-Treated Subjects	Table	ITT
14.2.14.1.4	Graphical Representation of Time to Symptom Response by Symptom Relief Medication Use, Placebo-Treated Subjects	Figure	ITT
14.2.14.2.1	Analysis of Time to Ability to Perform All Normal Activities by Symptom Relief Medication Use, Placebo-Treated Subjects	Table	ITTI
14.2.14.2.2	Graphical Representation of Time to Ability to Perform All Normal Activities by Symptom Relief Medication Use, Placebo-Treated Subjects	Figure	ITTI
14.2.14.2.3	Analysis of Time to Ability to Perform All Normal Activities by Symptom Relief Medication Use, Placebo-Treated Subjects	Table	ITT
14.2.14.2.4	Graphical Representation of Time to Ability to Perform All Normal Activities by Symptom Relief Medication Use, Placebo-Treated Subjects	Figure	ITT
14.2.14.3.1	Analysis of Proportions Experiencing Complications of Colds by Symptom Relief Medication Use, Placebo-Treated Subjects	Table	ITTI
14.2.14.3.2	Analysis of Proportions Experiencing Complications of Colds by Symptom Relief Medication Use, Placebo-Treated Subjects	Table	ITT
Safety Displays			
14.3.1.1	Summary of All Treatment Emergent Adverse Events	Table	ITT
14.3.1.2	Number and Percent of Subjects with Treatment Emergent Adverse Events by System Organ Class and Preferred Term	Table	ITT
14.3.1.3	Number and Percent of Subjects with Treatment Emergent Adverse Events by System Organ Class, Preferred Term and Severity	Table	ITT
14.3.1.4	Number and Percent of Subjects with Grade $\geq 3$ Treatment Emergent Adverse Events by System Organ Class and Preferred Term	Table	ITT
14.3.1.5	Number and Percent of Subjects with Treatment Emergent Adverse Events by System Organ Class, Preferred Term and Relationship to Study Medication	Table	ITT
14.3.1.6	Number and Percent of Subjects with Treatment Emergent Unexpected Adverse Events by System Organ Class and Preferred Term	Table	ITT

Display Number	Title	Type	Analysis Population
14.3.1.7	Number and Percent of Subjects with Treatment Emergent Serious Adverse Events by System Organ Class and Preferred Term	Table	ITT
14.3.1.8	Number and Percent of Subjects with Treatment Emergent Adverse Events Leading to Study Withdrawal by System Organ Class and Preferred Term	Table	ITT
14.3.2.1	Summary of Hematology Laboratory Results and Changes from Baseline	Table	ITT
14.3.2.2	Change in Hematology Laboratory Results Over Time: Shift Table	Table	ITT
14.3.3.1	Summary of Serum Biochemistry Laboratory Results and Changes from Baseline	Table	ITT
14.3.3.2	Change in Serum Biochemistry Laboratory Results Over Time: Shift Table	Table	ITT
14.3.4.1	Number and Percent of Subjects with Each Urinalysis Result	Table	ITT
14.3.4.2	Change in Urinalysis Results Over Time: Shift Table	Table	ITT
14.3.5.1	Summary of Vital Signs Results and Change from Baseline	Table	ITT
14.3.5.2	Change in Vital Signs Results Over Time: Shift Table	Table	ITT
14.3.6.1	Summary of Physical Examination Results by Category	Table	ITT
14.3.6.2	Number and Percent of Subjects with Physical Examination Changes from Normal at Baseline to Abnormal by Category	Table	ITT

*Listings*

16.2.1	Listing of Discontinued Subjects	Listing	ITT
16.2.2	Listing of Subjects with Protocol Deviations	Listing	ITT
16.2.3	Listing of Subjects Excluded from Efficacy Analysis	Listing	ITI
16.2.4.1	Listing of Demographic Data	Listing	ITT
16.2.4.2	Listing of Baseline Disease Characteristics	Listing	ITT
16.2.4.3	Listing of Prior Medication	Listing	ITT
16.2.4.4	Listing of Concomitant Medication	Listing	ITT
16.2.4.5	Listing of Medical History	Listing	ITT
16.2.4.6	Listing of Concomitant Diseases	Listing	ITT
16.2.5	Listing of Treatment Exposure Data	Listing	ITT
16.2.6.1	Listing of Time to Symptom Response	Listing	ITI
16.2.6.2	Listing of Time to Ability to Perform All Normal Activities	Listing	ITI
16.2.6.3	Listing of Complications of Colds	Listing	ITI
16.2.6.4	Listing of Time to Individual Symptom Response	Listing	ITI
16.2.6.5	Listing of Time to FLU-PRO Domain Response	Listing	ITI
16.2.6.6	Listing of Time to Return to Usual Health	Listing	ITT
16.2.6.7	Listing of Time to Symptom Response for All Subjects Treated	Listing	ITT

Display Number	Title	Type	Analysis Population
16.2.6.8	Listing of Time to Symptom Response for Specific Virus Subgroups	Listing	ITT
16.2.6.9	Listing of Virology Data	Listing	ITT
16.2.7	Listing of Adverse Events	Listing	ITT
16.2.8.1	Listing of Hematology Laboratory Results	Listing	ITT
16.2.8.2	Listing of Serum Biochemistry Laboratory Results	Listing	ITT
16.2.8.3	Listing of Urinalysis Laboratory Results	Listing	ITT
16.2.8.4	Listing of Plasma Tizoxanide and Tizoxanide Glucuronide Results	Listing	ITT
16.2.9.1	Listing of Vital Signs Data	Listing	ITT
16.2.9.2	Listing of Physical Examination Data	Listing	ITT
